4.2.1.2 Apraglutide Dose Adjustments, Interruptions and Stopping Rules

For subjects who do not tolerate the protocol dosing schedule, dose adjustments, or interruptions are mandated to allow the subjects to continue the trial medication and maintain apraglutide dosing for optimal treatment of aGVHD. The objective of these dose adjustment rules is to optimize response for each individual subject while avoiding clinically relevant toxicities attributed to apraglutide.

Dose reductions should be undertaken as outlined in Table 5.

Table 5: Dose Reduction Steps for Apraglutide

Original dose (mg)	2.5	4	5	7.5	10
New dose (mg)	0	2.5	4	5	7.5

Deviations to the recommended dose reductions, temporary interruptions, or permanent interruptions will need to be documented.

Subjects who are receiving multiple oncological treatments, or are dependent on parenteral support, develop abnormal liver function tests. In both cases bilirubin, ALT,

and/or AST may be elevated at baseline; therefore, the stopping rules for these subjects will use the increase from baseline instead of values from the ULN.

Table 6 depicts the dose adjustments for apaglutide dose in case of deviations of clinical safety parameters starting from Week 1.

Table 6: Apaglutide Dose Adjustments—Holding and Stopping Rules

Total bilirubin elevated (adapted from MAGIC)	
Use x ULN if normal at baseline (BSL) or x BSL if elevated at BSL	
>1.5–3.0 x ULN or BSL	Recommendation: Maintain dose level
>3.0–5.0 x ULN or BSL	
Mandatory: reduce by 1 dose level
 
Monitor LFTs weekly, or more frequently if clinically indicated, until resolved to $\leq 3.0 \times$ ULN/BSL:
 
 • If resolved in ≤ 14 days, then return to initial dose level • If resolved in >14 days, then maintain the dose level minus 1
>5.0–10.0 x ULN or BSL	
Mandatory: Hold dosing
 
Monitor LFTs weekly, or more frequently if clinically indicated, until resolved to $\leq 3.0 \times$ ULN/BSL:
 
 • If resolved in ≤ 14 days, then resume at initial dose level • If resolved in >14 days, then resume at dose level minus 1

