>10.0 x ULN or BSL	
Mandatory: Hold dosing
 
Monitor LFTs weekly, or more frequently if clinically indicated, until resolved to $\leq 3.0 \times$ ULN/BSL:
 
 • If resolved in ≤ 14 days, then resume at dose level minus 1 • If resolved in >14 days, then STOP dosing 
The subject should be further monitored weekly (including LFTs), or more frequently if clinically indicated, until total bilirubin has resolved to baseline or stabilization over 4 weeks

AST or ALT elevated (normal BSL)	
>5.0–<8.0 x ULN for more than 2 weeks	
Mandatory: Hold dosing
 
Repeat LFTs as soon as possible, preferably within 48–72 hours from awareness of the abnormal results; monitor LFTs weekly, or more frequently if clinically indicated, until resolved to $\leq 5.0 \times$ ULN.
 
Then:
 
 • If resolved in ≤ 14 days (which start after 2 weeks of elevation), then resume at initial dose level • If resolved in >14 days (which start after 2 weeks of elevation), wait for resolution to ULN then resume at dose level minus 1

$\geq 8.0 - \leq 20.0 \times \text{ULN}$	
Mandatory: Hold dosing
 
Repeat LFTs as soon as possible, preferably within 48–72 hours from awareness of the abnormal results; monitor LFTs weekly, or more frequently if clinically indicated, until resolved to $\leq \text{ULN}$
 
Then resume at dose level minus 1

$>20.0 \times \text{ULN}$	Mandatory: STOP dosing
AST or ALT elevated (elevated at BSL)	
$>3.0 - <5.0 \times \text{BSL}$	
Mandatory: Hold dosing
 
Repeat LFTs as soon as possible, preferably within 48–72 hours from awareness of the abnormal results; monitor LFTs weekly, or more frequently if clinically indicated, until resolved to $\leq \text{BSL}$.
 
Then:
 
 • If resolved in ≤ 14 days, then resume same dose level • If resolved in >14 days, wait for resolution to BSL then resume at dose level minus 1
$\geq 5.0 - \leq 20.0 \times \text{BSL}$	
Mandatory: Hold dosing
 
Repeat LFTs as soon as possible, preferably within 48–72 hours from awareness of the abnormal results; monitor LFTs weekly, or more frequently if clinically indicated, until resolved to $\leq \text{BSL}$.
 
Then resume at dose level minus 1.

$>20.0 \times \text{BSL}$	Mandatory: STOP dosing
Combined AST/ALT and bilirubin elevation	
Use $\times \text{ULN}$ if normal at BSL or $\times \text{BSL}$ if elevated at BSL	

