ALT/AST $>3.0 \times \text{ULN/BSL}$ and total bilirubin $>2.0 \times \text{ULN/BSL}$	
Mandatory: Hold dosing
 
Assess causality of the investigational compound:
 
 • If relationship to apaglutide is suspected (definitely, probably, possibly related) Stop dosing • If another cause is identified manage with institutional guidance and restart treatment
Asymptomatic amylase and/or lipase elevation	
$>1.0 - 1.5 \times \text{ULN}$	Recommendation: Maintain dose level
$>1.5 - 2.0 \times \text{ULN}$	Recommendation: Maintain dose level
$>2.0 - 5.0 \times \text{ULN}$	
Recommendation: Hold dosing until resolved to Grade ≤ 2, then:
 
 • If resolved in ≤ 7 days, then resume at same dose level • If resolved in >7 days, then resume at dose level minus 1
$>5.0 \times \text{ULN}$	Recommendation: Stop dosing
Pancreatitis	

Grade 2	Recommendation: Maintain dose level
Grade ≥ 3	Mandatory: Stop dosing
New onset of abdominal pain or worsening from BSL	
Grade ≥ 3	Mandatory: Stop dosing

ALT=alanine aminotransferase; AST=aspartate aminotransferase; BSL=baseline; LFT=liver function test; MAGIC=Mount Sinai Acute Graft Versus Host Disease International Consortium; ULN=upper limit of normal

Additional visits for unscheduled laboratory samplings or for safety reasons can be arranged as per the Investigator's judgment. In case of abnormal laboratory results of Common Terminology Criteria for Adverse Events (CTCAE) Grade 3 or higher assessed at a subject's local doctor, a re-assessment should be scheduled at the site.

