#### 4.3.8.4 *Clinical Laboratory Tests*

Blood and urines samples for safety analysis of clinical chemistry, including liver enzymes, hematology, hemostasis, and urinalysis parameters will be obtained as specified in the Schedule of Assessments (Table 1 and Table 2 of the protocol) and processed using local laboratory. Albumin, calprotectin, microbiome and blood markers analysis will be processed by central laboratory. For purposes of analysis and reporting, laboratory values will be standardized using the International System of Units (SI).

Clinical Laboratory evaluation results will be compared to laboratory reference ranges, with those values outside of the applicable range flagged as high or low. All local laboratory reports will be reviewed by the Investigator and parameters out of normal range assessed as “clinically significant” or “not clinically significant”.

All available clinical laboratory evaluations will be summarized descriptively by apraglutide dose levels and in total using descriptive statistics (n, arithmetic mean, median, minimum, and maximum) for hematology and chemistry laboratory parameters including absolute measurements and changes (absolute and percentage) from baseline by scheduled time points.

Abnormal laboratory results will be graded according to NCI-CTCAE version 5.0 as applicable. For some laboratory tests, the CTCAE criteria may include qualifying definitions (e.g., clinical AE and/or requirement for concomitant medication) in addition to the specific laboratory value used for the definition of the toxicity grades. For such tests, the qualifying definitions will not be used for the assignment of toxicity grades.

A shift table, presenting the 2-way frequency tabulation for baseline and the worst post-treatment value over the course of the trial according to the NCI-CTCAE grade will be provided for selected clinical laboratory tests including ALT, AST, total bilirubin, creatinine, amylase, lipase, GGT, GFR and hemoglobin. Both scheduled and unscheduled post-treatment visits will be considered in tabulation of the worst post-treatment value.

Additionally, the number and percentage of subjects with the following potentially clinically significant abnormal liver function test at post-baseline will be presented:

- ALT  $\geq 3 \times \text{ULN}$ ,  $\geq 5 \times \text{ULN}$ ,  $\geq 10 \times \text{ULN}$ , and  $\geq 20 \times \text{ULN}$

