- AST  $\geq 3 \times \text{ULN}$ ,  $\geq 5 \times \text{ULN}$ ,  $\geq 10 \times \text{ULN}$ , and  $\geq 20 \times \text{ULN}$
- Total bilirubin  $\geq 2 \times \text{ULN}$
- Potential Hy's Law cases: ALT or AST  $> 3 \times \text{ULN}$ , total bilirubin  $\geq 2 \times \text{ULN}$ , and ALP  $< 2 \times \text{ULN}$  at the same visit

A listing of subjects with any Potential Hy's Law cases ordered chronologically will be presented. The listing will include the visits at which the Potential Hy's Law cases were met, with the value of the following collected parameters: ALT, AST, Total bilirubin, and ALP.

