9. **In Germany**, only colonoscopies or MR enterography can be performed to detect polyps (not CT colonography). At screening, historical data are allowed where the colonoscopy/CT colonography/ MR enterography was performed within 6 months prior to the screening visit
10. The screening and Day 56 lower GI biopsy samples are optional and should be obtained only if the subject is medically suitable for the procedure. If lower GI biopsy was not obtained at screening, the Day 56 lower GI biopsy is not required. Historical lower GI biopsies collected at clinical diagnosis of lower GI-aGVHD are allowed to be used to confirm eligibility (if a biopsy is needed to rule out other reasons for diarrhea) and further trial analysis
11. If screening and randomization occur on the same day, historical ECG results obtained within 48 hours can be used. If randomization is done within 48 hours from screening, ECG does not need to be repeated
12. Vital signs (blood pressure, heart rate, temperature) will be recorded before apraglutide administration at each treatment visit
13. Height is to be measured at screening only
14. For females of childbearing potential, serum pregnancy tests will be performed at screening and baseline. At all other visits, only a urine pregnancy test will be performed
15. Hematology, hemostasis, clinical chemistry, and urinalysis. At dosing visits (Weeks 5, 7, 9–12, 14–16, 18–20, 22–25), only bilirubin is collected
16. Samples can be taken within 48 hours prior to randomization. Creatinine clearance must be estimated (the estimated globular filtration rate) within 48 hours prior to randomization to determine subject eligibility. At all the other visits, only serum creatinine will be assessed
  - c. If screening and randomization occur on the same day, historical local lab results obtained within 48 hours can be used
  - d. If randomization occurs within 48 hours from screening, local lab results do not need to be repeated
17. For subjects with a positive historical serology result post-transplantation for Epstein-Barr virus, cytomegalovirus, severe acute respiratory syndrome coronavirus 2 (SARS-CoV-2), human immunodeficiency virus (HIV), hepatitis B virus, or hepatitis C virus. A sample must be collected within 7 days prior to randomization/Day 0
18. This sample can be taken within 48 hours prior to randomization
19. Pre-dose PK samples should be taken within 2 hours before IMP administration is administered at Weeks 1, 2, 3, 4, 6, and 8

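### The potential Hy's law count requires all liver criteria at one visit, yet 16 of 25 weekly dosing visits schedule bilirubin only

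*SAP*

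**What the plan says.** SAP 4.3.8.4 (Clinical Laboratory Tests) defines a potential Hy's law case by three criteria: ALT or AST >3 x ULN, total bilirubin ≥2 x ULN and ALP <2 x ULN. All three must be met "at the same visit". The listing has the same scope: "The listing will include the visits at which the Potential Hy's Law cases were met". Elsewhere in that section ALT, AST and bilirubin thresholds are tabulated separately. For the shift tables, "Both scheduled and unscheduled post-treatment visits will be considered in tabulation of the worst post-treatment value".

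The SAP takes its liver samples from the protocol schedule; they "will be obtained as specified in the Schedule of Assessments (Table 1 and Table 2 of the protocol"). Footnote 15 to that schedule, repeated under SAP Table B1, reads: "At dosing visits (Weeks 5, 7, 9–12, 14–16, 18–20, 22–25), only bilirubin is collected". Follow-up visits have full panels.

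Protocol 4.2.1.2, Table 6, sets the dosing rules. Its combined rule (ALT/AST >3 x and bilirubin >2 x ULN or baseline) requires a hold followed by the step "Assess causality of the investigational compound". It has no same-visit condition. For a normal baseline, the lowest row for ALT/AST alone is ">5.0–<8.0 x ULN for more than 2 weeks". For bilirubin at ">1.5–3.0 x ULN or BSL" the only instruction is to keep the dose.

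**The concern.** The enzyme and bilirubin rises in drug-induced liver injury need not coincide. If bilirubin follows ALT/AST by one or two weeks, it may be detected at a visit where no ALT, AST or ALP is scheduled. If the enzymes have fallen to 3 x ULN or below by the next panel, no visit meets all three criteria and the subject is not counted.

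The separate threshold rows and the worst-value shift tables do not show that both rises occurred in the same subject. The potential Hy's law row is the one laboratory output that makes this link. A subject could also be held under the protocol's combined rule and be absent from the SAP's count, which would be awkward to explain in the report of a safety trial with about 34 subjects.

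**Working it through.** The plan states no figure to reproduce, so the check has three parts.

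**1. Visit counts (Table 1 and Table B1, footnote 15).** Full panels fall at Weeks 1, 2, 3, 4, 6, 8, 13, 17 and 21, then Week 26. Bilirubin-only visits are Weeks 5 and 7 (2), 9–12 (4), 14–16 (3), 18–20 (3) and 22–25 (4): 2 + 4 + 3 + 3 + 4 = 16. With the 9 full-panel visits this makes 25.

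- Bilirubin-only share of post-baseline dosing weeks: 2/7 to Week 7, 6/12 to Week 12, 16/25 to Week 25.
- Days between successive full panels from Week 1: 7, 7, 7, 14, 14, 35, 28, 28, 35.
- Longest look-back from a bilirubin-only visit to the previous panel: 28 days (Week 12 to Week 8, and Week 25 to Week 21).

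**2. Do the repeat-test rules close the gap?** Partly. Bilirubin above 3.0 x ULN or baseline requires weekly liver tests. ALT/AST of 8 x ULN or more, or above 3 x an elevated baseline, requires a hold with repeat tests (above 20 x, dosing stops). For a normal baseline, ALT/AST of 3–5 x ULN has no row of its own, the next band acts only after more than two weeks, and bilirubin of 2–3 x ULN triggers no repeat. Protocol 6.5 asks for close monitoring without a schedule, and extra sampling under 4.2.1.2 is at the investigator's judgement.

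Example: ALT 4 x ULN at Week 8, bilirubin 2.5 x ULN at Weeks 10 and 11, both resolved by Week 13. The same-visit rule finds no case. Pairing by date finds one: Week 8 with Week 10 (14 days) or Week 11 (21 days).

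**3. Illustration of size (all time courses assumed).** ALT/AST is >3 x ULN over days [t, t+D). Bilirubin is ≥2 x ULN over [t+L, t+L+B), with B = 14 or 28. Onset t is uniform over days 56–175, dosing runs to Week 25, bilirubin is sampled weekly and there are no unscheduled tests. A case is observable if a full panel shows the enzyme rise and a bilirubin sample 0–28 days later shows the bilirubin rise. It is left out if no single panel shows both.

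Share left out = (observable cases with no panel showing both) / (observable cases). Ranges are over the two values of B.

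| Bilirubin lag L | D = 14 days | D = 21 | D = 28 | D = 42 |
|---|---|---|---|---|
| 7 days | 43% | 27% | 20–27% | 6–27% |
| 14 days | not informative* | 60% | 43% | 6–43% |

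*The two rises do not overlap, so every case is left out by construction.

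For example, with L = 7 and D = 14, 41.3% of onsets are observable and 17.7% are observable but left out: 17.7/41.3 = 43%.

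With onset in days 0–56, dosing continued and a 7-day lag, the share is 37% for D = 14 and 12% for D = 21. For a subject in complete response at Week 8, with no bilirubin-only visits afterwards, it is 29% for D = 14 and zero for D ≥ 21. With a 14-day lag that subject's share is about one third for D = 21 and zero for D ≥ 28.

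**The case against.** The strongest reply is that the gap is narrow and the percentages overstate it. The illustration assumes no unscheduled liver tests, although Table 6 requires them for larger rises, and its main table uses the least favourable schedule. Dosing beyond Week 12 is limited to subjects without complete response whom the investigator expects to benefit, and to flare re-treatment. This stands as a limit on size: the figures are conditional shares under assumed time courses and not a forecast.

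A second reply is that a held subject is still reported. Protocol 6.6.2 requires the safety reason for a dose reduction or pause to be recorded as an adverse event. The SAP then tabulates dose modifications (4.3.6.1), events leading to interruption (4.3.8.1.2) and a broad hepatic query (4.3.8.3). This also stands in part, but those outputs depend on an event being reported and coded, and they do not pair laboratory values. Nor does the combined rule's silence on timing prove a conflicting definition; it shows only that the SAP adds a condition the protocol does not state.

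A third reply is that a wider rule will bring in other causes. Entry permits ALT/AST up to 8 x ULN, and liver GVHD is itself staged on bilirubin. That is true. It is a reason to keep the same-visit count and to show liver stage and baseline beside the added one.

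**Conclusion.** The concern holds. From scheduled samples, 16 of the 25 weekly dosing visits cannot yield a potential Hy's law case, and the mandatory repeats leave a definite hole for a normal-baseline subject with a moderate enzyme rise followed by bilirubin of 2–3 x ULN. Under the stated assumptions the share of observable staggered cases left out ranges from zero (complete response at Week 8, longer enzyme rise) to 60% (late dosing, 14-day lag). The number of subjects affected cannot be estimated, because the documents give no event rate, and many staggered cases would still be caught. Table 6 and the safety committee work independently of this row. The point is worth considering because it bears on the primary objective and costs little to put right; it does not invalidate the safety analysis.

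**What to change.** Keep the same-visit count and add one further count and listing to SAP 4.3.8.4. Using all scheduled and unscheduled values and the sample date (SAP 4.1.1 names every extra visit Unscheduled, so visit name is not a safe key), pair ALT or AST >3 x ULN, with ALP <2 x ULN on that sample, with total bilirubin ≥2 x ULN on the same day or within a pre-stated window afterwards. A window of 28 days would reach every bilirubin-only visit from the preceding panel; its length is a judgement. For each listed subject show the full ALT, AST, bilirubin and ALP course from baseline and the MAGIC liver stage, so that liver GVHD and raised-baseline cases can be recognised.

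The cost is one table row and one listing from data already collected. The downside is that some additional subjects, including some whose bilirubin rise is liver GVHD, will need medical review.

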#### *4.3.8.5 Vital Signs*

Descriptive statistics will be provided for systolic blood pressure, diastolic blood pressure, heart rate. Changes from baseline to scheduled visit and the minimum, maximum, and last post-baseline values will be presented. Both scheduled and unscheduled post-baseline values will be considered for summaries of the minimum, maximum, and last post-baseline values.

The number and proportion of subjects with potentially clinically significant changes in vital signs will be presented based on the following thresholds:

- Systolic blood pressure  $\geq 160 \text{ mmHg}$  and increase  $\geq 20 \text{ mmHg}$  from baseline
- Systolic blood pressure  $\leq 90 \text{ mmHg}$  and decrease  $\geq 20 \text{ mmHg}$  from baseline
- Diastolic blood pressure  $\geq 100 \text{ mmHg}$  and increase  $\geq 15 \text{ mmHg}$  from baseline
- Diastolic blood pressure  $\leq 50 \text{ mmHg}$  and decrease  $\geq 15 \text{ mmHg}$  from baseline
- Heart rate  $\geq 120 \text{ bpm}$  with increase  $\geq 15 \text{ bpm}$  from baseline
- Heart rate  $\leq 50 \text{ bpm}$  with decrease  $\geq 15 \text{ bpm}$  from baseline

#### *4.3.8.6 Electrocardiograms*

Twelve-lead electrocardiogram parameters (Hearth rate (HR),pulse rate (PR), PR interval, RR interval, QRS duration, QT, QTcF interval) will be summarized by apraglutide dose levels and in total using descriptive statistics for actual values and for changes from baseline by scheduled time of evaluation, including the last post-baseline and the maximum post-baseline value. Both scheduled and unscheduled post-treatment values will be considered for summaries of the last and maximum post-baseline values.

The overall clinical assessment of the ECG readings is recorded for clinical significance. Shift tables from baseline to the worst post-baseline result will be presented by apaglutide dose levels. The following categories will be used, from worst to best-case: Abnormal clinically significant, Abnormal not clinically significant, Normal.

In addition, subjects experiencing QTcF elevation or change from baseline will be tabulated by visit for each scheduled post-baseline evaluation and at any time post-baseline (including unscheduled visits) for minimum, maximum, and last post-baseline value, for the following (sub)categories:

- QTcF elevation
  - QTcF > 450 ms
  - QTcF > 480 ms
  - QTcF > 500 ms
- Increase from baseline
  - Increase from baseline QTcF > 30 ms
  - Increase from baseline QTcF > 60 ms

Subcategories are mutually exclusive, subjects are counted once in the worst category.

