## 4 STATISTICAL METHODOLOGY

### 4.1 General Considerations

Unless otherwise specified, continuous data will be summarized descriptively by apraglutide dose group (High Dose, Low Dose, Total Randomized, Low Body Weight, Total) and by time point. Descriptive statistics for continuous variables will include: the number of subjects, mean, standard deviation (sd), median, first and third quartiles (Q1, Q3), minimum, and maximum. All raw data will be presented to the original number of decimal places. Where appropriate, mean, median, and confidence interval will be presented to one more decimal, while standard deviation will be reported to two more decimals.

Unless otherwise specified, categorical data will be summarized descriptively by apraglutide dose group (High Dose, Low Dose, Total Randomized, Low Body Weight, Total) and time point. Summary statistics for categorical variables will contain counts and percentages. The numbers and percentages of missing data for a variable will be reported when applicable. Percentages will be reported to one decimal except for zero and one hundred percent, which will be presented as 0% and 100%, respectively; unless otherwise specified, the percentages are based on the number of subjects in the respective analysis set. Two-sided 95% confidence intervals for single proportion will be estimated via Clopper-Pearson exact method.

Analyses will be performed using SAS® (version 9.4 or higher, SAS Institute Inc., Cary NC.) and/or R (version 4.1.0 or higher, R Foundation for Statistical Computing, Vienna, Austria). When possible, note that the preferred use of methods: Hyndman and Fan's Definition 2 (1996) for quantiles estimation, "half away from zero" for rounding.

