#### 4.2.4 *Safety Analysis Set 2*

Safety Analysis Set (SAS2) comprises all the subjects included in FAS and exposed to at least one dose of apaglutide. All safety analyses will be carried out on the SAS2 according to the actual dose of apaglutide received (if a subject receives both dose levels during the course of the trial, this subject will be assigned to the High Dose group). Supportive safety analyses will be carried out on the SAS2.

When analyses are displayed in a single layout for both SAS1 and SAS2 (using a 5-column format), this document will refer to analysis on “SAS”.

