#### 4.3.8 *Primary Endpoints*

Safety analysis will be performed by Dose levels (Low Dose, High Dose, Total Randomized, Low Body Weight, Total), on the SAS.

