**Table B1: Schedule of Assessments - Screening, Baseline, Treatment, and Optional Treatment**

Assessments	Screening 	Baseline /First dose	Treatment visits Week 1 – Week 7 								Treatment visits Week 8 – Week 12		Optional Treatment visits  If no CR at Week 13					
											In case of no CR at Week 8 							
Visit No. IRT/eCRF use	1	2	3	4	5	6	Dosing	7	Dosing	8	Dosing	9	Dosing	10	Dosing	11	Dosing	
Week		0	1	2	3	4		5	6	7	8	9, 10, 11, 12	13	14, 15, 16	17	18, 19, 20	21	22, 23, 24, 25
Day		0	7	14	21	28	35	42	49	56		91		119		147		
Visit Window 	-84 to -1 days	0	±1 day	±1 day	±1 day	±1 day	±1 day	±1 day	±1 day	±1 day	±1 day	±1 day	±1 day	±1 day	±1 day	±1 day	±1 day	
General																		
Informed consent	X																	
Inclusion and exclusion criteria	X	X																
RUX start 		X																
Randomization 		X																
Demographics	X																	
Medical, surgical and disease history	X																	
Prior and concomitant medication	X	X	X	X	X	X	X	X	X	X	X	X	X	X	X	X	X	
Hospitalization status	X	X	X	X	X	X	X	X	X	X	X	X	X	X	X	X	X	
Safety																		
Colonoscopy/CT colonography/ MR enterography 	X																	
Lower GI biopsy 	X										X							
Physical examination	X	X	X	X	X	X		X		X		X		X		X		X
Twelve-lead ECG 	X	X																
Vital signs 	X	X	X	X	X	X		X		X		X		X		X		X
Body weight and height 	X	X	X	X	X	X	X	X	X	X	X	X	X	X	X	X	X	
Adverse events	X	X	X	X	X	X	X	X	X	X	X	X	X	X	X	X	X	

Assessments	Screening 	Baseline /First dose	Treatment visits Week 1 – Week 7 								Treatment visits Week 8 – Week 12		Optional Treatment visits  If no CR at Week 13					
													Lower GI-aGVHD flare treatment after CR is achieved 					
Visit No. IRT/eCRF use	1	2	3	4	5	6	Dosing	7	Dosing	8	Dosing	9	Dosing	10	Dosing	11	Dosing	
Week		0	1	2	3	4	5	6	7	8	9, 10, 11, 12	13	14, 15, 16	17	18, 19, 20	21	22, 23, 24, 25	
Day		0	7	14	21	28	35	42	49	56		91		119		147		
Visit Window 	-84 to -1 days	0	±1 day	±1 day	±1 day	±1 day	±1 day	±1 day	±1 day	±1 day	±1 day	±1 day	±1 day	±1 day	±1 day	±1 day	±1 day	
Pregnancy test 	X	X				X				X		X		X		X		
Local labs 	X	X 	X	X	X	X	Bilirubin only	X	Bilirubin only	X	Bilirubin only	X	Bilirubin only	X	Bilirubin only	X	Bilirubin only	

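### QTcF outlier percentages default to the whole safety set, so subjects with no post-baseline ECG count as non-outliers, and without early discontinuation the first scheduled post-baseline ECG is at Week 26

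*SAP*

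**What the plan says.** **Denominator.** SAP 4.1 sets a general rule for categorical summaries: "unless otherwise specified, the percentages are based on the number of subjects in the respective analysis set". The same paragraph adds: "The numbers and percentages of missing data for a variable will be reported when applicable". SAP 4.3.8.6 states that "subjects experiencing QTcF elevation or change from baseline will be tabulated by visit for each scheduled post-baseline evaluation and at any time post-baseline", and includes unscheduled visits in the any-time summary. It gives no denominator of its own.

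**Analysis set.** SAP 4.3.8: "Safety analysis will be performed by Dose levels (Low Dose, High Dose, Total Randomized, Low Body Weight, Total), on the SAS". SAS2 "comprises all the subjects included in FAS and exposed to at least one dose of apaglutide"; SAS1 is the randomized counterpart. Neither requires an ECG.

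**ECG schedule.** SAP Table B1 marks ECGs at screening and baseline only. Table B2 leaves Weeks 8, 13, 17 and 21 blank. It marks Weeks 26, 52 and 104 and the two early-discontinuation visits. The early treatment discontinuation visit is 4 weeks (+1 week) after the last dose. Protocol 5.8.5 also allows clinically indicated ECGs during treatment.

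**Timing of analyses.** Under SAP 1, the Primary Analysis has a clinical cut-off of up to 01 Dec 2023, when all subjects have reached Day 91 or withdrawn, and it supports the CTR. Endpoints are analysed at both the Primary and EOT steps unless stated otherwise. SAP 4.3.8.7 restricts physical examination to the EOT analysis. Nothing similar is said for ECG.

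**The concern.** A subject with no post-baseline ECG cannot be recorded as a QTcF outlier, yet under the default rule stays in the denominator. The percentage then mixes how often QTcF was raised with how often anyone looked. The SAP deals with this elsewhere. Biomarker summaries (4.3.10.6) are limited to subjects with evaluable baseline and post-baseline samples, and the response analyses (4.3.9) drop censored visits from the visit denominator. The ECG section has neither rule.

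The second issue is timing. The any-time row can combine an ECG taken one dosing interval after a dose with one taken more than four months after the last dose, and nothing in the table separates them.

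Safety is the primary objective, and clinically significant ECG change is a listed safety endpoint. A low or zero QTcF percentage in the CTR could be read as reassurance on all dosed subjects when it rests on fewer, and partly on ECGs recorded well after exposure.

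**Working it through.** The plan states no figure for ECG coverage or expected QTcF percentages, so there is nothing to reproduce. The check is schedule arithmetic and a denominator comparison.

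**Step 1: last dose to Week 26 ECG (Day 182), nominal days.** Last-dose weeks come from SAP 2.1. Gap = 182 − 7 × (week of last dose).

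| Last dose | Day | Gap to Week 26 ECG |
|---|---|---|
| Week 7 (main treatment) | 49 | 182 − 49 = 133 days |
| Week 12 (extension) | 84 | 182 − 84 = 98 days |
| Week 25 (optional or flare) | 175 | 182 − 175 = 7 days |

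SAP 4.3.8.1 ends the treatment-emergent period 28 days after the last dose. Day 182 − 28 = Day 154 (Week 22), so the Week 26 ECG falls inside that period only when dosing continued to Weeks 22–25.

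**Step 2: earlier scheduled ECGs.** The early treatment discontinuation ECG is 28 to 35 days after the last dose. After a last dose at Week 4 (Day 28), for example, that is Day 56–63. It precedes Week 26 for any last dose up to Week 20 (140 + 35 = 175 < 182). The early trial discontinuation ECG is timed from the discontinuation date.

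**Step 3: Primary Analysis.** 01 Dec 2023 − 91 days = 01 Sep 2023. 01 Dec 2023 − 182 days = 02 Jun 2023. By nominal days, a subject first dosed after 02 Jun and by 01 Sep 2023 has reached Day 91 but has no Week 26 ECG due. Such a subject, and anyone who died before Week 26, has no post-baseline ECG unless a discontinuation-visit or unscheduled ECG was recorded.

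**Step 4: effect on the percentage.** The documents do not give the number evaluable, so the values of n below are assumptions. Reported share = x/N and share among those observed = x/n, with x = 2 outliers. With x = 0, the one-sided 95% upper bound is 1 − 0.05^(1/n).

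| Evaluable n (of N = 34) | 2/34 | 2/n | Upper bound if x = 0 |
|---|---|---|---|
| 34 | 5.9% | 5.9% | 8.4% |
| 26 | 5.9% | 7.7% | 10.9% |
| 17 | 5.9% | 11.8% | 16.2% |

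The ratio N/n is 1.00, 1.31 and 2.00. For the 30 randomized subjects, 2/30 = 6.7% compares with 2/15 = 13.3% if half are evaluable.

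**The case against.** The strongest reply has four parts.

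- **Missing data stay visible.** SAP 4.1.2 says missing values are not imputed and descriptive statistics use observed values. SAP 4.1 provides for missing counts, from which a reader could recover the evaluable n. The denominator is only a default, and table specifications sit in a separate document (SAP 5). This stands in part. However, the missing counts are promised only when applicable, and showing one does not change the printed percentage.
- **Other ECGs exist.** Discontinuation-visit and clinically indicated ECGs can fall before Week 26, and unscheduled ones count in the any-time row. This stands. A reader might infer that no subject has an ECG scheduled before Week 26. The documents support that only for subjects who do not discontinue early.
- **Some Week 26 ECGs are close to dosing.** After a Week 25 dose the gap is 7 days. A reader might infer that many subjects lack an ECG, or that most ECGs are off drug. The documents give no counts by dosing duration or ECG coverage, so neither can be asserted.
- **ECG safety is covered elsewhere.** The shift table of overall ECG assessment and adverse event reporting also bear on the endpoint, and the QTcF table is descriptive. This limits the consequence but does not correct the table.

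A reader might also take the 51.0% six-month survival in Protocol 1.1 to mean that 49% of subjects would be unobserved. That figure comes from a different, single-arm ruxolitinib trial. It would be an upper bound on the loss from deaths alone, requiring that no such subject had a discontinuation-visit or unscheduled ECG.

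**Conclusion.** The concern holds in this form. Followed as written, SAP 4.1 and 4.3.8.6 count subjects without a post-baseline ECG as non-outliers. The Primary Analysis is open to this even for surviving, compliant subjects, because its trigger is Day 91 and the first routine post-baseline ECG is at Day 182. The dilution factor is N/n, and n is unknown: it is 1.31 if 26 of 34 are evaluable and 2.00 if 17 are. The any-time row also pools ECGs at very different distances from the last dose without showing it.

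The conclusion assumes that the separate table specifications do not already replace the default denominator. It also relies on SAP Tables B1 and B2, which Appendix B presents as corresponding to protocol Tables 1 and 2. The ECG row of protocol Table 1 is not reliably aligned in the available text and should be confirmed against them. The point should be corrected, but it concerns one descriptive safety display and no formal test.

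**What to change.** Amend SAP 4.3.8.6 as follows.

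1. **Denominator.** For the any-time summary, use subjects with at least one evaluable post-baseline ECG. For the increase-from-baseline categories, also require a baseline ECG. For each visit, use subjects with an ECG at that visit. Print this n in every column.
2. **Time since last dose.** Present results by days from last dose to ECG, and state where the 28–35 day discontinuation ECG falls. One workable split is up to 28 days (matching the treatment-emergent window in SAP 4.3.8.1), 29–35 days, and later.
3. **Footnote.** State that no routine ECG was scheduled during the dosing weeks. The wording should not imply that Week 26 is an on-treatment visit, since for many dosing courses it is not.

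The cost is a wording change and one derived variable (days since last dose), with small cells in some time bands. No additional ECG is required. If the Primary Analysis tables already exist, the same denominators can be added there and the change reported in the CTR under Protocol 7.9.
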